Based on these preliminary findings, we propose the following model, which is consistent with the top-down inhibition hypothesis. According to this model, individuals in an anxious state experience worrisome thoughts that can potentially distract them from ongoing tasks (especially those that require central executive processes). When task demands are high, cognitive control processes (mediated by the dlPFC) filter out these worrisome thoughts. By filtering out these worrisome thoughts, these cognitive control processes reduce anxiety, as well as the impact of anxiety on ongoing task performance. Individuals who are unable to engage these cognitive control processes are less able to reduce their anxiety and are therefore more likely to be negatively impacted by their anxiety.

2. Study Objectives

a. Primary objectives

The primary objective of this study is to determine whether altering activity in the FPN with TMS will reduce anxiety either alone (during NPU) or during a low load cognitive task (Sternberg WM).

3. Subjects

a. Description of study populations

The study will be conducted in 184 healthy volunteers. The participants will be adult males and females, aged 18 to 50. We will begin with a 10 subject pilot phase to determine the minimum interval between the TMS probe and the startle probe necessary to recover usable APS data. The target number of completers for each experiment will be N=48 for a total of 144 completers. We anticipate that about 15% of subjects (N=121) will either terminate the study during the task because of discomfort. An additional 9 subjects (3 per experiment) will be included for piloting. To account for this projected attrition rate, we aim for an accrual of 184 medically and psychiatrically healthy volunteers including the 10 pilot subjects. The participants will be adult males and females, aged 18 to 50. The accrual ceiling is 184. Subjects may participate in multiple sub-studies, and will be consented each time they are asked to participate in a given sub-study. NIH employees may participate. NIMH employees and staff and their immediate family members will be excluded from the study per NIMH policy.

b. Inclusion criteria

- Ages 18-50
- Subjects able to give their consent
- Right handed

c. Exclusion criteria

- Non-English speaking individual
- Any significant medical or neurological problems (e.g. cardiovascular illness, respiratory illness, neurological illness, seizure, etc.)

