Prior to the study visits, the participants will have been screened and cleared under the 01-M-0254 screening protocol. Healthy volunteers will first participate in the MRI visit in the NMR center. The consent form will be signed at the beginning of the MRI visit. Immediately after the consent form is signed, the subject will complete the TMS safety screen (TASS). Subjects who do not meet the criteria for TMS will be withdrawn from the study at this time. Subjects participating in multiple sub-studies will complete the MRI visit only when participating in their first sub-study, unless the MRI visit needs to be repeated. Subjects in Sub-study 3 will also receive TMS sensation screen. During this screen, subjects will receive a single train of 4 mA electric scalp stimulation matching the frequency and duration of the study visit TMS. No actual TMS will be delivered during this visit. The subjects will then be asked whether they would be willing to tolerate this level of scalp stimulation during the TMS sessions. Subjects who are unable or unwilling to continue will be withdrawn from the study at this time. Subjects will be compensated for the MRI visit whether or not they wish to discontinue after the tolerability screen. Next, we will collect at T1, a T2, and a diffusion-weighted echo-planar image using an available 3T scanner. Next subjects will undergo a single run of resting state and a single run of the Sternberg task, without shocks, probes, or TMS pulses to serve as functional localizers to identify a FPN stimulation site for TMS. Subjects who need clinical scans will receive those as well. All procedures are solely for research purposes.

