Subjects will be informed that they can withdraw from the study whenever they wish. Sample shocks will be administered prior to the study. At this point, subjects will be explicitly asked if they wish to continue. Subjects receiving the frontal TMS will also be given a chance to experience the sensation of the TMS via electric scalp stimulation. Subjects will be given the opportunity to discontinue after this sensation screen. The experiment will also be stopped for any subject who exhibits signs of distress during any phase of the study. Subjects will be constantly monitored via closed circuit video by the AI for MRI sessions. An AI is present during TMS sessions. A credentialed staff member (RN, NP or MD) will assess the subject at the conclusion of the study or at any time if significant side effects develop. The subject will be withdrawn at any time if unable to follow the rules for participation in this study.

9. Outcome Measures

a. Primary outcome measures

The primary outcome measures will be APS reduction as a function of stimulation type, active or sham stimulation.

10. Statistical Analysis

a. Analysis of data/ study outcomes

Sternberg. APS scores will be created by subtracting the startle magnitude during the safe blocks from the startle magnitude during the threat blocks. These scores will be analyzed using a 2 [block: active vs. sham] x 2 [stimulation: TMS vs. no TMS] x 2 [interval: maintenance vs. ITI] repeated measures ANOVA.

NPU. APS scores for the cue and ITI will be created by subtracting the startle magnitude during the safe blocks from the startle magnitude during the unpredictable blocks. FPS scores will be calculated by subtracting the startle magnitude during the predictable ITI from the startle magnitude from the predictable cue. These scores (APS cue, APS ITI, FPS cue) will be analyzed using a 2 [block: active vs. sham] x 2 [stimulation: TMS vs. no TMS] repeated measures ANOVA.

b. Power analysis

In our Sternberg pilot experiment, we obtained the effect size ($f=0.72$) for our observed WM load-related decrease in anxiety. Assuming a somewhat smaller effect size ($f=0.5$) due to regression to the mean, if we set power at .95 and experiment-wise, two-tailed alpha at 0.05. Based on these parameters, we will need 48 subjects per experiment. Assuming a 15% unusable data rate and 3 subjects to initially adjust the experimental procedure, we will need 58 subjects per experiment.

11. Human Subjects Protection

a. Subject selection

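### The 15% attrition allowance is misprinted (N=121 for 21) and taken on completers, so 184 accrued gives about 140 expected completers, not 144; post-consent screen withdrawals have no stated place in the count

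*Combined protocol and SAP*

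**What the plan says.** Section 3.a (Description of study populations) builds the accrual from these parts:

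- Completers: "The target number of completers for each experiment will be N=48 for a total of 144 completers".
- Loss: "We anticipate that about 15% of subjects (N=121) will either terminate the study during the task because of discomfort".
- Set-up subjects: "An additional 9 subjects (3 per experiment) will be included for piloting".
- Total: "To account for this projected attrition rate, we aim for an accrual of 184 medically and psychiatrically healthy volunteers including the 10 pilot subjects", followed by "The accrual ceiling is 184".

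Section 10.b (Power analysis) reaches the per-experiment figure with the same percentage under a different label: "Assuming a 15% unusable data rate and 3 subjects to initially adjust the experimental procedure, we will need 58 subjects per experiment".

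Section 4.d (Study procedures, General) places two exit points after consent, at the MRI visit. The first is the TMS safety questionnaire (TASS), for all subjects: "Subjects who do not meet the criteria for TMS will be withdrawn from the study at this time". The second is the scalp-sensation screen, for sub-study 3 only: "Subjects who are unable or unwilling to continue will be withdrawn from the study at this time".

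**The concern.** Three things in the sample-size paragraph do not fit together.

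1. The printed count of 121 cannot be 15% of anything in the plan.
2. The allowance is described as a share of subjects, but it was computed as a share of completers. That always gives too few places, because the loss acts on everyone who enters.
3. Subjects withdrawn at the TASS or the sensation screen have signed this protocol's consent but have not started the task. Neither description of the 15% (stopping during the task in 3.a, unusable data in 10.b) clearly covers them.

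At stake is whether the accrual ceiling delivers the 48 completers per experiment on which section 10.b rests its power statement. Sub-study 3 has the only sensation screen, so it is the experiment most exposed to unplanned loss.

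**Working it through.** **Inputs.** From 3.a: 144 completers (48 x 3), 15% loss, 9 set-up subjects, 10 pilot-phase subjects, ceiling 184. From 10.b: 48 completers per experiment, 15%, 3 set-up subjects, 58 per experiment.

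**Reproducing the plan's figures.** The plan multiplies completers by (1 + loss rate).

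- Per experiment: 48 x 1.15 = 55.2, taken as 55; 55 + 3 = 58; 3 x 58 + 10 = 184.
- Overall: 0.15 x 144 = 21.6, taken as 21; 144 + 21 + 9 + 10 = 184.

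Both routes match exactly. So 21 is the intended count. The printed 121 would be 84% of 144, 73% of 165 or 66% of 184.

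**What 184 delivers at 15% loss among entrants.**

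- Entrants to the main experiments: 184 - 10 - 9 = 165 (55 each).
- Expected completers: 165 x 0.85 = 140.25, or 55 x 0.85 = 46.75 per experiment.
- Shortfall: 144 - 140.25 = 3.75, which is 3.75/144 = 2.6%.
- Loss that the allowance covers: 21/165 = 12.7% (7/55 per experiment).

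**Chance of still reaching the target** (binomial, independent entrants, true loss exactly 15%).

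- At least 144 of 165: 0.24.
- At least 48 of 55 in a given experiment: 0.40.
- At least 48 in all three: 0.40477 cubed = 0.07.

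**For scale only.** Dividing by (1 - loss rate) would give 144/0.85 = 169.4, so 170 entrants and 170 + 9 + 10 = 189. Per experiment it gives 48/0.85 = 56.5, so 57 + 3 = 60, and 3 x 60 + 10 = 190. The plan is 5 to 6 places below this.

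**Effect on power.** Section 10.b does not name the test behind its 48. As an illustration, reading f = 0.5 as a standardised paired difference with two-sided alpha 0.05, power is 0.924 at 48, 0.919 at 47 and 0.913 at 46. This reading needs 54 subjects for 0.95, so it does not reproduce the plan's 48. It shows only that one or two completers fewer changes power by about 0.01.

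**Post-consent screens.** The documents give no failure rate for either one. They also do not say whether a withdrawn subject uses a place under the ceiling or may be replaced. To show the range only, assume that such subjects count and that the full 15% applies afterwards. A TASS failure rate of 0 to 10% in all subjects, with 0 to 20% declining at the sensation screen in sub-study 3, then gives 140 down to 118 expected completers. A 10% loss at the sensation screen alone gives (110 + 49.5) x 0.85 = 135.6. These are not estimates for this trial.

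**The case against.** A reader might infer that 144 completers cannot be reached, or that the screens will push the total well below 140. The documents support neither.

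- The loss is given as approximate. At exactly 15% there is still about a 24% chance of reaching 144, and the expected gap is 2.6%.
- Volunteers are cleared under 01-M-0254 before the MRI visit (section 4.c), with medical, medication and family history and a check of the eligibility criteria. Section 3.c already excludes seizure history, epilepsy in self or first-degree relatives, stroke, brain surgery, head injury, cranial metal and drugs that lower the seizure threshold. The TASS looks for much the same risk factors (section 7.b), so few cleared volunteers may fail it.
- People who decline at the sensation screen may be those who would later have stopped for discomfort. Taking the full 15% afterwards may count them twice.
- It is not stated that screen withdrawals use up accrual.
- Section 3.a lets subjects join several sub-studies. If 184 counts persons, 5 to 6 repeat entries would close the gap before any screen loss.
- The loss sentence in 3.a is visibly incomplete (the word either has no alternative), so the scope of the 15% is ambiguous and not clearly confined to the task.

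Most of this stands, and it limits the point. It does not remove the misprint, the wrong base or the silence about screen withdrawals. Nor can the plan rely on repeat participation while the Précis says that each subject is assigned to one sub-study only.

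**Conclusion.** The sample-size paragraph is wrong as written, by a modest amount. N=121 should read 21, and 21 is 15% of completers. At the plan's own rate, the 184 ceiling gives about 140 expected completers (46 to 47 per experiment) against a stated 144 (48 each). The allowance covers 12.7% loss, not 15%.

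This assumes that each subject enters one sub-study, that the 9 set-up and 10 pilot subjects are separate and not analysed, and that 15% is the total loss among entrants. Any further loss at the TASS or the sensation screen is unquantified and may be small. The defect there is that the plan does not say how such withdrawals count.

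**What to change.** 1. In 3.a, correct 121 to 21 and complete the broken sentence.
2. In 3.a and 10.b, either restate expected completers under the 184 ceiling as about 140 (46 to 47 per experiment at 15% loss), or state that 58 per experiment tolerates at most 12.7% loss if 48 are to complete.
3. In 10.b, name the test behind the sample size and give the power at 46 to 47 completers, so that the requirement for 48 is not left standing beside a smaller expected number.
4. State whether the 15% means task termination, unusable data or both.
5. State whether subjects withdrawn after consent at the TASS or the sensation screen count against the ceiling or may be replaced, and report their number separately by sub-study.
6. Reconcile 3.a (several sub-studies allowed) with the Précis (one only), and say whether 184 counts persons or entries.

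The cost is protocol wording, one power recalculation and a slightly less favourable stated figure. No added enrolment is needed, and no study procedure has to move.

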TMS pulses evoke transient eyeblink responses due to stimulation of the scalp: In a recent pilot, we tested the effect of TMS pulses on eyeblink responses. Given that our primary outcome measure is startle, we wanted to ensure that stimulation of the scalp muscles did not interfere with our ability to record startle evoked eyeblinks. We found that TMS pulses (in a 5 Hz train) indeed induce twitches in the orbicularis oculi muscle. However, these twitches were small, and the EMG signal recovered within 150 ms of the TMS pulse (See Figure 13). When comparing the TMS evoked eyeblink to the acoustic startle reflex, it is clear that the TMS evoked eyeblink has an earlier onset, and a shorter duration than the acoustic startle reflex. This difference is likely due to the origin of the two blinks. The TMS evoked blink arises due to direct stimulation of the orbicularis

oculi, while the blink evoked by the startle probe arises through the CNS via engagement of the acoustic startle reflex arc (Blumenthal et al., 2005).

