At a more mechanistic level, we can identify 3 possible mechanisms whereby the TMS pulse may affect the acoustic startle response: 1) The TMS pulse may interfere with the ability of the acoustic startle reflex to activate the fibers innervating the orbicularis oculi. We do not believe this will be an issue because orbicularis oculi EMG activity returns to baseline within 150 ms of the TMS pulse, which is well below the minimum interval between the TMS pulse and the subsequent startle probes; 2) The TMS pulse may trigger prepulse inhibition, which is the reduction of startle due to an unexpected preceding stimulus. We do not believe this will be an issue because prepulse inhibition is maximal at 120 ms and no longer exist after ~500 ms, which again is well below the minimum interval between the TMS pulse and the subsequent startle probes (Hoffman and Fleshler, 1963; Larrauri and Schmajuk, 2006); 3) The TMS pulse may reduce the predictability of the startle probe, thereby reducing the likelihood/amplitude of the startle response. We do not believe this will be an issue because we startle probes in many of our other experiments are somewhat predictable (e.g. the NPU threat paradigm; See Schmitz & [name], 2012). We also plan to vary the interval between the TMS pulse and the startle probe using timing parameters that have shown to be effective in previous studies (Balderston et al., 2015, 2016a). In addition, if such an effect would occur, it would be balanced across conditions.

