We have made every possible effort to account for the non-specific effects of scalp stimulation by TMS on our dependent measure. First, it is important to note that our dependent measure in these studies is not the raw startle magnitude, rather it is the change in startle magnitudes during periods of safety and threat, and that the stimulation will be balanced across these conditions. Therefore, any non-specific effect of scalp stimulation on blink magnitude should be eliminated in the difference score. Furthermore, the current generated by the e-stim placebo coil is similar in magnitude, duration, and distribution to the current induced by the TMS pulse (Borckardt et al., 2008; Gonz, Strauss, & Schwerdtfeger, 2011; Rossi et al., 2007; Sheffer et al., 2013). In addition, electrically and magnetically stimulated blinks are nearly identical to each other in topology (Blumenthal et al., 2005). Together, these observations suggest that any non-specific effects of scalp stimulation on blink magnitude should be similar for the sham and TMS conditions.

These results suggest that it will be possible to record startle evoked eyeblinks given a sufficient interval between the TMS train and startle probe.

Summary: Our preliminary data show the following:

- 1) Anxiety interferes with WM performance, only during a task that requires central executive resources.
- 2) WM load is sufficient to reduce anxiety whether or not the WM task engages central executive resources.
- 3) Even during low load tasks, threat of shock activates the dlPFC.
- 4) Anxiety patients show impaired performance and reduced dlPFC activity relative to healthy controls during the n-back task.
- 5) Threat of shock increase cortical excitability in the parietal cortex, and this hyperexcitability may mediate the hypervigilance seen in anxious patients.

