Participants who are cleared to continue are invited to participate in the study. Screening results are regularly discussed with the research team at the weekly clinical meetings. Information obtained under the 01-M-0254 screening protocol may be used for research data in this protocol. [name], Medical Advisory Investigator, will ultimately be medically responsible for the enrollment of each subject in the study.

d. Study procedures

Pilot phase: We will begin with an ~10 subject pilot study to determine the parameters necessary to recover usable APS data following a TMS probe. In this pilot study we will present startle probes following no stimulation (control), a TMS pulse, and a sham pulse (with electrical stimulation of the scalp). Pulses will be administered at 100% of the MEP threshold, and delivered to the motor cortex site used to determine the motor threshold, so as to minimize the potential for CNS-based startle reduction. We will then measure the effect of this stimulation on raw startle magnitude, and APS. Importantly, we will vary the duration between the TMS/sham pulses and the acoustic startle probe to identify the minimum pulse/probe interval needed to recover usable APS data. This minimum threshold, anticipated to be ~1 second, will be used in all future studies.

General: As mentioned in “Study overview,” subjects in sub-studies 1 and 2 will participate in 2 outpatient visits (1 MRI visit and 1 TMS visit). where they will be assigned to one of two sub-studies (NPU or WM) for the TMS visit. Subjects in sub-study 3 will participate in 3 outpatient visits (1 MRI visit and 2 TMS visits). Visits will be separated by ~1 week (no more than 2 weeks), according to the subject’s availability.

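### The pilot's pulse-to-probe minimum, anticipated at about 1 s, leaves no permissible probe time inside the continuous 1 Hz blocks of Sub-studies 1 and 2, and no rule limits the probe relative to the next pulse

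*Combined protocol and SAP*

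**What the plan says.** Section 4.d, Pilot phase, plans about 10 subjects in whom the gap between a TMS or sham pulse and the acoustic probe is varied "to identify the minimum pulse/probe interval needed to recover usable APS data". The result is then carried forward: "This minimum threshold, anticipated to be ~1 second, will be used in all future studies".

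Section 4.d, Sub-studies 1 and 2, and its TMS paragraph describe uninterrupted 1 Hz pulses over the left IPS for the whole of each TMS-on block. Probes fall in those same blocks, placed by task period: maintenance or ITI in Sub-study 1, cue or ITI in Sub-study 2. The sham coil gives its scalp pulse at the same moment as each magnetic pulse, so sham blocks have the same cycle. Section 4.a describes delivery differently, at random times in the NPU task or on randomly chosen working-memory trials.

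Section 1.c gives the supporting figures. From an earlier recording it reports: "We found that TMS pulses (in a 5 Hz train) indeed induce twitches" in the eye muscle, and that "the EMG signal recovered within 150 ms of the TMS pulse". It adds that "prepulse inhibition is maximal at 120 ms and no longer exist after ~500 ms". It treats both effects as safely shorter than the minimum pulse-to-probe gap. On timing it says "We also plan to vary the interval between the TMS pulse and the startle probe", with parameters from two cited earlier studies but no values in the text. It concludes that startle blinks can be recorded "given a sufficient interval between the TMS train and startle probe".

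**The concern.** Two parts of Section 4.d cannot both be followed at the protocol's own anticipated figure. A probe inside a 1 Hz train is always less than 1 s after the last pulse, unless it coincides with the next one. A 1 s minimum therefore excludes every probe in the TMS-on blocks.

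A somewhat shorter minimum removes the strict impossibility but pushes the probe towards the following pulse. Section 1.c reports that each pulse itself makes the eye muscle twitch, and the blink is recorded from that muscle. The plan says how soon after a pulse a probe may come, but not how long before the next pulse it must come.

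APS is the primary outcome, and the TMS-on cells are half of the design analysed in Section 10.a. Once probes have been delivered they cannot be re-timed.

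**Working it through.** **Inputs.** Anticipated minimum about 1 s (4.d, Pilot phase). Pulse rate 1 Hz, uninterrupted within a block (4.d, Sub-studies 1 and 2, TMS). EMG recovery 150 ms and end of prepulse inhibition about 500 ms (1.c). Trial counts from 4.d. The 1 s is an expected pilot result, so no formula reproduces it.

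**Window per cycle.** The pulse interval is 1/(1 Hz) = 1,000 ms. For a minimum of m ms after the preceding pulse, the permitted window is max(0, 1,000 − m). This is also the longest possible gap from a permitted probe to the next pulse.

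| m (ms) | Window, preceding pulse only: 1,000 − m | Window if the next pulse must also be at least 150 ms after the probe: max(0, 850 − m) |
|---|---|---|
| 150 | 850 | 700 |
| 500 | 500 | 350 |
| 800 | 200 | 50 |
| 900 | 100 | 0 |
| 1,000 | 0 | 0 |

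The last column is illustrative. The documents give no blink-scoring interval, so the protocol's 150 ms EMG recovery time is borrowed as an assumption. On that assumption the window closes at m = 850 ms.

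**Trials affected, Sub-study 1.** The stated total reproduces: 2 × 2 × 2 × 2 × 2 × 2 × 3 = 192, or 4 runs × 4 blocks × 12 trials = 192. Two of the four blocks in each run are TMS-on: 4 × 2 × 12 = 96 trials, 48 active and 48 sham. These form 2 (active/sham) × 2 (threat/safe) × 2 (maintenance/ITI) = 8 cells of 12 probes.

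**Trials affected, Sub-study 2.** Half the trials are TMS-on, which is 96 of the stated 192. The stated total needs the three threat conditions counted as 3 (2 × 3 × 2 × 2 × 2 × 4 = 192). The factors as printed give 2 × 2 × 2 × 2 × 2 × 4 = 128. The block description gives (16 predictable + 16 unpredictable + 8 neutral) × 4 runs = 160. The affected half is therefore 64, 80 or 96.

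**Sub-study 3.** Probes come in NPU runs before and after offline stimulation, so the conflict does not arise.

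**Hypothetical only: probes not timed to pulses.** If the pilot's rule were not enforced and probes fell uniformly over the cycle (assumption), the share inside the minimum would be m/1,000: 50% at 500 ms and 90% at 900 ms. Each Sub-study 1 cell would keep on average 12 × 0.50 = 6 or 12 × 0.10 = 1.2 compliant probes.

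**The case against.** The strongest reply is that 1 s is a forecast. What binds later studies is the pilot's result, and 150 ms and about 500 ms both point to something shorter, at which a 1 Hz cycle has usable time. This stands, and it makes the contradiction conditional on the pilot. It does not make the anticipated figure workable. The 150 ms also describes recovery from the pulses themselves; probes within a train were not what was reported.

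Second, the plan does treat the gap as controlled: Section 4.d carries a minimum into all later studies, and Section 1.c speaks of a minimum and of a varied interval. This also stands. A reader might infer that the plan has no timing rule, and so that half or more of the TMS-on probes will be lost. The documents do not support that. Naming task periods for probes does not show that probes ignore pulses within those periods, and the loss figures apply only if the plan's own rule is broken. What is missing is narrower: a stated range, and a limit on the side of the next pulse.

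Third, Section 1.c argues that effects balance. APS is threat minus safe, stimulation is balanced across both, and it expects that "any non-specific effects of scalp stimulation on blink magnitude should be similar for the sham and TMS conditions". This protects the active-versus-sham contrast from bias to the extent that the scalp effects match. It does not create a permitted window where there is none.

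Finally, Section 4.a could be read as intermittent stimulation. It gives no pulse-to-probe timing and conflicts with the per-block trains of Section 4.d, so it is one more passage to reconcile.

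**Conclusion.** The conflict is real at the protocol's anticipated value. With pulses 1,000 ms apart and a 1 s minimum, the permitted window is zero. None of the 96 TMS-on trials in Sub-study 1, and none of the TMS-on half of Sub-study 2, can comply. This rests on an uninterrupted 1 Hz train and probes inside it, as Section 4.d describes. That arithmetic is certain; the consequence at any shorter minimum depends on the pilot.

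For shorter minimums a window exists, but it is bounded on one side only. How much of it is usable depends on a blink-scoring interval that the documents do not state.

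A reader might go further and conclude that the TMS versus no-TMS factor is confounded with closeness to a pulse, or that the active-versus-sham result is biased. The first would need probes inside the minimum to be delivered and kept, contrary to Section 4.d. The second would need sham and active scalp effects to differ, where Section 1.c expects them to be similar. Neither is shown. The point should be settled before Sub-studies 1 and 2 begin.

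**What to change.** Before Sub-studies 1 and 2 start, reconcile the timing statements in Section 1.c, the delivery described in Section 4.a, and the pilot, Sub-study 1, Sub-study 2 and TMS paragraphs of Section 4.d. The stimulation settings remain the sponsor's decision.

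Then state a probe window for TMS-on blocks with three parts:

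- the probe comes at or beyond the pilot's minimum after the preceding pulse;
- blink scoring, with its interval written down, is complete before the next pulse;
- the distribution of probe times within the cycle is the same for threat and safe and for active and sham.

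If the pilot's minimum leaves no such window, the conflict must be resolved before those sub-studies begin.

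The cost is one timing rule in the protocol and the matching change to the probe script. The downside is less freedom to jitter probes within the pulse cycle.
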